### 6.5.1 RESCUE THERAPY

Patients may use rescue therapies as recommended by their CPP provider or other physician as part of usual care. The only additional rescue intervention to be initiated directly by the study team is to assess for severe depression at time of questionnaire submission (baseline, 3-month, 6-month). If a patient screens positive for severe depression (defined by score >70 on PROMIS Depression SF 8b), they will receive a call from a study member who will complete a brief screen for suicidal ideation. If positive, the patient will be referred to the University of Michigan Psychiatric Emergency Service. If no suicidal ideation, we will offer referral to University of Michigan Depression Center or offer to contact the patient's PCP to help facilitate evaluation and treatment.

## 7 STUDY INTERVENTION/EXPERIMENTAL MANIPULATION DISCONTINUATION AND PARTICIPANT DISCONTINUATION/WITHDRAWAL

### 7.1 DISCONTINUATION OF STUDY INTERVENTION/EXPERIMENTAL MANIPULATION

After patients are randomized to group and complete baseline questionnaire, we will not discontinue access to the intervention for the duration of the 6-month study period, despite new medical/psychiatric diagnoses including pregnancy or undergoing gynecologic surgery. Patients may elect to withdraw from the study as described below.

### 7.2 PARTICIPANT DISCONTINUATION/WITHDRAWAL FROM THE STUDY

Patients may choose to withdraw from the study at any time. If a patient withdraws before the 3-month questionnaire is sent, we will attempt to replace them with another eligible patient

### 7.3 LOST TO FOLLOW-UP

Patients will receive an email with a link to questionnaires and utilizations surveys at each time point specified above. If questionnaires are not completed within 4 days, an automatic reminder email will be

sent. If questionnaires are not completed within 7 days, a study member will call with a reminder. If questionnaire is not completed with 14 days, a study member will call with another reminder. Patient will be considered lost to follow up if they fail to complete the 6-month questionnaire within 21 days after survey invitation.

We will not exclude or dismiss patients based on completion of 6-month questionnaire or monthly utilization survey as these are not essential for the primary outcome.

## 8 STUDY ASSESSMENTS AND PROCEDURES

### 8.1 SCREENING PROCEDURES

We will be using thoughtful recruitment and allocation methods to minimize bias. Our group of specialty-trained gynecologists see approximately 150 patients per month in this referral clinic. Each returning patient will receive a brochure containing a brief description of the study and an interest sheet during their check-in. A physician may assess interest if they feel that the patient may be an appropriate candidate. A study team member will also screen patients scheduled for return visits in the clinic and contact potentially eligible patients via text or email to inform them that they may be eligible for the study. We will not recruit new patients during this pilot study as patients often initiate a number of new treatments following the initial visit and we suspect that it might be more challenging to differentiate effect of the intervention versus treatment plan in this population.

A study team member will contact interested patients to assess eligibility and confirm interest and obtain consent (electronic). Potential subjects will be contacted up to seven times (by telephone, text, portal message, or email) in order to establish contact. Entry as a subject requires passing a telephone screen to confirm eligibility.

### 8.2 STUDY EVALUATION AND PROCEDURES

Once eligibility and interest are confirmed, the study team member will send an email link to an electronic version of the consent form. The study team member and patient will review study consent verbally over the telephone and answer any questions. Consent forms describing in detail the study intervention, study procedures, and risks will be given to the participant. Consent forms will be signed and stored electronically. We have elected to perform this combination of verbal and online consent as opposed to a face-to-face consent as the majority of patients from our referral clinic travel between 1-4 hours to reach our clinic. One of goals of this intervention is to expand access and limit barriers related to travel that our patients typically encounter. Therefore, we felt that requiring subjects to return for a visit specifically for a face-to-face consent would impose too great a burden for many participants, and that this approach was reasonable given the remote contact utilized in other aspects of this study.

Random allocation will occur in 2:1 ratio (intervention:control) utilizing permuted blocks of 4 without stratification. Allocation concealment will be ensured using computer generated central randomization and will occur after patient has signed the consent form. The study team member who generates random allocation sequence will not be involved in recruitment or enrollment. Patients will be blinded to their group assignment. Study team members involved in outcome assessment will be blinded to

group assignment. The patient's specialty gynecologist who will continue to provide usual care for pelvic pain will also be blinded to group assignment.

Enrollment will occur on a rolling basis until 69 patients have been enrolled. We anticipate that we will likely need to screen approximately 200 patients in order to enroll 69 participants over an 18-month period. We will attempt to recruit a diverse group of patients, with attention to diversity in race, ethnicity, age, education level, rural vs urban locality, sexual orientation, and gender identification.

Following enrollment, patients will complete online baseline questionnaires, which will include current treatments for pelvic pain symptoms (medications, physical therapy, etc.). After completing questionnaires, patients in the intervention group will receive access to the intervention website and those in the control group will receive access to the symptom monitoring website.

### *Intervention group*

Patients in the intervention group will receive access to the *My Pelvic Plan* website (<https://www.mypelvicplan.com/>), which is a self-directed program which integrates patient education about conditions that frequently contribute to pelvic pain, as well as instruction on cognitive and behavioral restructuring, self-administration of acupuncture, engaging in physical activity, and a brief introduction to pelvic floor physical therapy techniques. They will have open access to the program over the 6-month intervention period. The intervention will be comprised of an active (12-week) phase and a maintenance (3-month) phase. During the active phase, we will use an established tailoring program to direct participants to particular modules or skills that are likely to be most relevant for their individual symptoms and characteristics. All intervention participants will receive a weekly text or email prompt directing them to a specific module. All participants will receive prompts to the same modules for the first four weeks of the study. During the next 8 weeks, participants will receive prompts to modules that corresponded to their most impactful symptoms on their baseline questionnaires. Following the 12-week active phase, all participants will enter the maintenance phase, during which they will receive monthly prompts to Monitoring Progress symptom tracker module.

Patients will have open access to the program over the 6-month intervention period. While they will receive text or email prompts to visit specific modules, they will ultimately choose how they navigate and utilize the program and we will not prescribe a specific schedule or utilization frequency.

We are unable to track website utilization for specific users. However, we will send an email link to a survey once per month which will ask which skills (from the *Managing Symptoms* section of the website) they used in the last month regardless of whether they visited that module in the site. We assume that some patients will need repeated exposure to skills to gain mastery and incorporate into their routine, whereas other patients may visit a module once and be able to incorporate it into regular practice.

Patients will receive a questionnaire battery at 3-month interval (primary endpoint) and 6-month interval (secondary endpoint). Patients will receive an email with a link to questionnaires at 3 months and again at 6 months. The 6-month questionnaire will also include questions regarding current treatments for pelvic pain symptoms, including interval surgery.

After completion of 3-month questionnaire battery, we will be performing focus groups for approximately one-half of the patients in the intervention group (n=20) in order to obtain in-depth feedback regarding the program. We will attempt to include an intentionally diverse group of

participants for these focus groups, with intentional recruitment to reflect diversity in age, race, geographic location and pelvic pain conditions. These sessions will focus on skills and modules that were most impactful and whether participants believe that combining the intervention with an individual coach or an online community might be beneficial.

#### *Control group*

Patients in the control group will undergo an active control intervention in which they receive open access to a separate website (<https://monitoringprogress.org/>) that contains only the Monitoring Progress symptom tracker subpage over the 6-month study period. Control group participation will also be divided into an active (12-week) phase and a maintenance (3-month) phase. Similar to the intervention group, the control group will receive a weekly text or email prompt directing them to track a specific symptom or activity during the active phase of that study. During the maintenance phase of the study, they will receive monthly prompts to the Monitoring Progress subpage (without prompting to a specific symptom or activity).

Control participants will receive a questionnaire battery at 3-month interval (primary endpoint) and 6-month interval (secondary endpoint).

Both patients in the intervention and control groups will receive contact from the study team at the same intervals throughout the study. If questionnaires are not completed within 4 days, an automatic reminder email will be sent. If questionnaires are not completed within 7 days, a study member will call with a reminder. If questionnaire is not completed with 14 days, a study member will call with another reminder. Patient will be considered lost to follow up if they fail to complete the 6-month questionnaire within 21 days after survey invitation. Both intervention and control groups will continue to follow with their specialty gynecologist and will receive usual care throughout the study period. On average, patients follow up every 3-4 months in this clinic per their physician recommendation and we will not recommend any specific changes to usual care follow up as part of this study.

A participant is considered to have completed the study if they have completed the baseline questionnaire and the 3-month questionnaire.

After completion of 3-month questionnaire, we will be performing focus groups for approximately one-half of the patients in the intervention group (n=20) in order to obtain in-depth feedback regarding the program and potential adjunct therapies for future studies. Patients in the intervention group may decline this invitation and still be considered to have completed the study.

The study will conclude once all patients have completed the final 6-month questionnaires. Patients may choose to withdraw from the study at any time. If a patient withdraws before the 3-month questionnaire is sent, we will attempt to replace them with another eligible patient.

### 8.3 SAFETY ASSESSMENTS

The study team will assess for severe depression at time of questionnaire submission (baseline, 3-month, 6-month). If a patient screens positive for severe depression (defined by score >70 on PROMIS Depression SF 4b), they will receive a call from a study member who will complete a brief screen for suicidal ideation. If positive, the patient will be referred to the University of Michigan Psychiatric

Emergency Service. If no suicidal ideation, we will offer referral to University of Michigan Depression Center or offer to contact the patient's PCP to help facilitate evaluation and treatment.

## 8.4 ADVERSE EVENTS AND SERIOUS ADVERSE EVENTS

### 8.4.1 DEFINITION OF ADVERSE EVENTS

This protocol uses the definition of adverse event from 21 CFR 312.32 (a): any untoward medical occurrence associated with the use of an intervention in humans, ***whether or not considered intervention related***.

This intervention is considered to carry low risk to subjects. Patients with chronic pelvic pain have episodic symptom exacerbations, which can sometimes be related to known triggers such as menses or intercourse, but often appear idiopathic or unpredictable. Additionally, patients with chronic pain conditions have higher rates of depression compared to their peers and we want to ensure that patients suffering from severe depression receive appropriate treatment.

Therefore, we will consider the following to be adverse events:

- Pain exacerbation prompting evaluation in emergency department
- Pain exacerbation prompting scheduled gynecologic surgery
- Screen positive for suicidal ideation in discussion with study team member following up on screen for severe depression

### 8.4.2 DEFINITION OF SERIOUS ADVERSE EVENTS

We will consider the following to be serious adverse events:

- Pain exacerbation prompting inpatient hospitalization
- Pain exacerbation prompting urgent or emergent surgical evaluation
- Suicide attempt or significant deterioration of psychiatric conditions resulting in inpatient psychiatric hospitalization

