## 2.3 RISK/BENEFIT ASSESSMENT

### 2.3.1 KNOWN POTENTIAL RISKS

*Breach of confidentiality:* Participation in this study poses a risk for breach of confidentiality. Several measures have been taken to reduce the risk of breach of confidentiality. These include training of study team members, electronic and physical security measures for data capture and storage and collecting a minimum of identifiable information for each individual project. Breach of confidentiality will be considered a “definitely related” Serious Adverse Event. As such, it will be reported to the University of Michigan IRB within 7 days of occurrence, and a remediation plan will be put in place immediately.

*Discomfort associated with being asked personal questions about health history and the completion of questionnaires:* Any participant becoming distressed while completing questionnaires will be encouraged to seek clarification of any questions that they find to be unclear or troubling. All participants are told that they have the option to terminate participation without penalty and/or will be assisted in arranging medical/ psychiatric help including, if necessary, emergency treatment if needed.

*Symptom exacerbation:* We do not anticipate that the *My Pelvic Plan* program is likely to place patients at an increased risk of symptom exacerbations. Cognitive and behavioral programs have been shown to be low risk for adverse events. However, we will discuss that new activities, such as physical therapy and exercise, sometimes precipitate a temporary increase in myofascial pain, and will offer basic anticipatory guidance. This is a well-described phenomenon and is not unique to this program. Our CPP provider have extensive expertise in determining whether exacerbations are typical given possible triggers and can offer individual guidance on whether additional evaluation is warranted.

During the study period, all patients will receive usual care as determined by their CPP provider and PCP. While we will not enroll patients who are planning to undergo surgery during the study period, patients will be able to proceed with any intervention determined to be necessary by their medical providers, including surgery and medication changes, without being excluded from our analysis. We will collect data on interim surgery or medication changes at the 3 and 6-month follow up periods.

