#### 8.4.4 TIME PERIOD AND FREQUENCY FOR EVENT ASSESSMENT AND FOLLOW-UP

The occurrence of an adverse event (AE) or serious adverse event (SAE) may come to the attention of study personnel during study visits and interviews of a study participant presenting for medical care, or upon review by a study monitor.

All AEs, not otherwise precluded per the protocol, will be captured on the appropriate case report form (CRF). Information to be collected includes event description, time of onset, clinician's assessment of severity, relationship to study procedures (assessed only by those with the training and authority to make a diagnosis), and time of resolution/stabilization of the event. All AEs occurring while on study will be documented appropriately regardless of relationship. All AEs will be followed to adequate resolution.

Any medical or psychiatric condition that is present at the time that the participant is screened will be considered as baseline and not reported as an AE. However, if the study participant's condition deteriorates at any time during the study, it will be recorded as an AE.

Changes in the severity of an AE will be documented to allow an assessment of the duration of the event at each level of severity to be performed. Documentation of onset and duration of each episode will be maintained for AEs characterized as intermittent.

Study coordinator will record events with start dates occurring any time after informed consent is obtained until 7 (for non-serious AEs) or 30 days (for SAEs) after the last day of study participation. At each study visit, the investigator will inquire about the occurrence of AE/SAEs since the last visit. We will primarily rely on patient self-report of adverse events and will not proactively search internal or external medical record systems to identify these. Events will be followed for outcome information until resolution or stabilization.

---

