#### 8.4.6 SERIOUS ADVERSE EVENT REPORTING

In consultation with the PI, a trained member of the study team will be responsible for conducting an evaluation of a serious adverse event and shall report the results of such evaluation to NIH and the

reviewing Institutional Review Board (IRB) as soon as possible, but in no event later than 10 working days after the investigator first learns of the event.

---

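### Section 8.4.2 lists three serious adverse events and names neither fatal nor life-threatening ones, so a grave event outside the list has no expedited deadline stated in the protocol.

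*Combined protocol and SAP*

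**What the plan says.** **Serious events (8.4.2).** After the lead-in "We will consider the following to be serious adverse events" come three items: "Pain exacerbation prompting inpatient hospitalization"; "Pain exacerbation prompting urgent or emergent surgical evaluation"; and "Suicide attempt or significant deterioration of psychiatric conditions resulting in inpatient psychiatric hospitalization". There is no catch-all and no general criterion of seriousness.

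**Adverse events (8.4.1, 8.4.4).** Section 8.4.1 takes the broad regulatory definition, any untoward medical occurrence whether or not related. It then continues "Therefore, we will consider the following to be adverse events" and lists an emergency-department visit for pain, scheduled gynecologic surgery for pain, and a positive screen for suicidal ideation. Section 8.4.4 is broad again: "All AEs occurring while on study will be documented appropriately regardless of relationship". It also makes any deterioration of a baseline condition an adverse event.

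**Grading (8.4.3.1).** The scale runs to 4 (life threatening or disabling) and 5 (fatal). It notes that severe and serious are not the same thing.

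**Reporting and recording.**
- SAEs go to NIH and the IRB as soon as possible and "in no event later than 10 working days after the investigator first learns of the event" (8.4.6).
- Other adverse events go to IRBMED as it requires, with no time given, and to NIH annually (8.4.5).
- Unanticipated problems that are SAEs have the same 10-working-day limit; other unanticipated problems go to the IRB and NIH annually (8.5.2).
- Events are recorded up to 30 days after last participation if serious and 7 days if not (8.4.4).

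**Breach of confidentiality (2.3.1).** This is called an SAE, and "it will be reported to the University of Michigan IRB within 7 days of occurrence". It does not appear in 8.4.2.

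**The concern.** SAE status decides how fast anyone outside the study team hears of an event and how long the team keeps recording. A definition made of three specific situations leaves the most serious outcomes to chance: they count only if they arise through pain or psychiatric illness in one of the listed ways. The plan foresees fatal and life-threatening events, because it grades them, but nothing ties those grades to seriousness.

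Such events are uncommon in a low-risk web programme but can be foreseen. The protocol screens for severe depression and suicidality, and participants who become pregnant or have surgery stay in the study (5.2, 6.5, 7.1).

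There is little to fall back on. Safety oversight rests with the investigator and the mentor (10.1.5), clinical monitoring is marked not applicable (10.1.6), and events are found mainly by self-report without a search of records (8.4.4). Self-report cannot bring a participant's own death to light. Prompt external reporting is thus the main independent check.

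**Working it through.** The plan gives no figure to reproduce. The check is to follow each kind of event through the definitions, the reporting rules and the recording window.

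| Event | Meets an 8.4.2 item? | Deadline stated in the protocol | Recorded after last participation |
|---|---|---|---|
| Death or life-threatening event in a pain-prompted admission or urgent surgical evaluation | Yes | 10 working days, NIH and IRB | 30 days |
| Suicide attempt | Yes; a fatal attempt by natural reading, though death is not named | 10 working days, NIH and IRB | 30 days |
| Death or life-threatening event by any other route | No | None to IRBMED beyond its own requirement; NIH annually | 7 days |
| Admission not prompted by pain or psychiatric illness | No | As the row above | 7 days |
| Breach of confidentiality | No, but an SAE under 2.3.1 | 7 days from occurrence to the IRB; 10 working days from awareness under 8.4.6 | 30 days |

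**Third row under each reading of 8.4.1.** On the broad definition the event is an adverse event, graded 5 or 4, and follows 8.4.5. On the three-item list it may not be an adverse event at all. Section 8.4.4 favours the broad reading, but two staff members could apply the same protocol and record different events.

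**Does the unanticipated-problem rule close the gap?** No. Its 10-working-day limit applies only when the problem is also an SAE. Otherwise reporting to the IRB and NIH is annual.

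**Recording window.** The difference is 30 − 7 = 23 days. An event that starts on days 8 to 30 after last participation and meets no listed item falls outside the recording period.

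**Notice to participants (8.4.7).** SAEs judged probably or definitely related are reported to participants within 60 days. All other events wait for up to a year after the study ends. A related grave event outside the list takes the slower route.

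**The two breach clocks.** Suppose a breach is discovered d days after it occurs. If d is below 7, a report by day 7 from occurrence also falls within 10 working days of awareness, so both limits can be met. If d exceeds 7, the limit in 2.3.1 has already passed at discovery while the limit in 8.4.6 is only starting. The clocks conflict only for a breach found late.

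**The case against.** The case for leaving the text alone has several sound parts, and each limits the point.

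- **Not every death is lost.** A reader might infer that all grade 5 events drop out of expedited reporting. They do not: a death in a pain-related admission meets a listed item, and a completed suicide is naturally read as a suicide attempt with a fatal outcome.
- **A fast IRB route may exist.** A reader might infer that these events have no expedited route at all. Section 8.4.5 defers to IRBMED's requirements, which the documents do not reproduce. What can be shown is that the protocol itself states no expedited deadline, and that its NIH report is annual.
- **The adverse-event definition is not simply cut to three items.** The broad definition comes first, and 8.4.3.1 and 8.4.4 fit it. This is a contradiction, not a clean restriction.
- **The SAE list is not treated as complete.** Section 2.3.1 adds a fourth SAE, and 8.4.2 does not say that it is exclusive. This shows inconsistency, but does not bring fatal or life-threatening events in.
- **No comparison of safety by arm is harmed.** A reader might infer that SAE counts by group would be incomplete. Section 9.4.4 plans no safety analysis, so no planned table is affected.
- **Hospitalisation of any cause.** A reader might infer that every admission must be an SAE. Nothing in the documents sets that threshold, and 8.4.1 treats scheduled gynecologic surgery for pain as a non-serious event, so such a rule could reclassify planned surgical admissions.

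None of this answers the central point: a fatal or life-threatening event outside the three items is not an SAE as the protocol is written.

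**Conclusion.** The point holds in a bounded form. It covers fatal and life-threatening events that meet no item in 8.4.2. For these the protocol states no expedited deadline: reporting to NIH is annual where it would be 10 working days for an SAE, reporting to IRBMED follows rules that are not given, and recording stops 23 days sooner. How many events this would affect among 69 participants cannot be derived from the documents; the number is probably small, but each would matter.

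This is a stated rule with the wrong result, not a missing detail, because the reporting limit, the recording window and the notice to participants all depend on SAE status. Two inconsistencies come with it: the broad and the narrow adverse-event wording in 8.4.1 and 8.4.4, and the breach of confidentiality that 2.3.1 calls an SAE and 8.4.2 leaves out.

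The conclusion assumes that 8.4.2 is applied as written and that no other document, such as the manual of procedures or IRBMED policy, supplies a wider definition. If one does, the protocol should cite it.

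**What to change.** 1. **8.4.2:** make the list non-exhaustive. State that any event graded 4 or 5 under 8.4.3.1 is an SAE, and keep the present items as examples. The grade 3 description also mentions potential threat to life, so the line between grades 3 and 4 should be made clear once SAE status depends on it.
2. **8.4.1:** introduce the three items with *including*, so that the section agrees with its own general definition and with 8.4.4.
3. **Breach of confidentiality:** list it in 8.4.2. Reconcile the limit counted from occurrence in 2.3.1 with the limit counted from awareness in 8.4.6, so that a breach found late has a deadline that can be met.
4. **Hospitalisation for other causes:** the sponsor should state whether it counts as serious, in a way consistent with how 8.4.1 treats scheduled surgery.

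The cost is an amendment to the wording and a few more events to record and report. The interventions, the sample size and the efficacy analysis do not change.
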